4.2.2.2 Imaging Procedures

CESR imaging involves a research ultrasound scanner as well as conventional b-mode ultrasound to guide the location of the imaging. The conventional ultrasound will be conducted just prior to CESR imaging for localization. Imaging will be performed within the package insert guidelines for ultrasound system mechanical index (a measurement of output power) when imaging perflutren contrast agent (less than 0.8).

CESR imaging will be performed by trained medical personnel using mild compression to eliminate motion. Total imaging time is estimated to be less than 15 minutes. All image data will be de-identified and transferred for off-line analysis based on a study ID. The research images will NOT be interpreted or analyzed for clinical decisions related to the patient. The field of view of the research images will be limited to clinically identified

lesions. Incidental findings are not anticipated due to the sensitivity limitations of this imaging modality. Information regarding additional lesions or other incidental findings discovered during research imaging procedures will not be recorded or communicated to the patient or their provider because this imaging modality is not standard of care.

4.2.3 Standard of Care Biopsy (if applicable)

The patient will then undergo his or her scheduled biopsy procedure based on the pre-study diagnostic imaging. The research CESR imaging will NOT be interpreted prior to the biopsy and therefore will not influence any clinical decision concerning the biopsy.

4.2.4 Medical Record Abstraction (if applicable)

The primary objective of this study is to determine the sensitivity and specificity of CESR imaging. In order to meet this objective, we will review each patient's clinical records, including their pathology report from biopsy. The malignancy will be determined as indicated by the pathology report.

4.2.5 Reader Study

[figure not shown]
A reader study will be performed after the completion of patient accrual to study lesion characteristics under CESR as compared to conventional b-mode ultrasound. In these pilot observational studies, the primary aim will be to evaluate the imaging approach for application in these two organs. We will also estimate the receiver operating characteristic (ROC) curve for the CESR system. For scientific rigor, a total of five readers who are not investigators on this study (radiologists trained in breast imaging or ultrasound imaging) will be recruited to participate for each reader study. The readers will be asked to assign a probability score (1 to 5) and confidence for each lesion for each modality (0 to 100%). ROC analysis will be performed as the primary analysis for the first aim. To compare the results from the two imaging modalities, we will adopt the mixed effect ANOVA based on the Dorfman-Berbaum-Metz method. The outcome variable is the Tukey's jackknife pseudovalues of the AUCs from each reader and each patient under either modality, and separately for each anatomic region. The fixed effect in the independent list will correspond to the difference between the two modalities, and the random effects will be used to account for within-patient and within-reader's correlations. Possible interactions between the modalities and the readers and the patients will also be included and tested for statistical significance. To test the main hypothesis, F-test statistic from the model parameter estimates will be used to compare the mean AUCs between the b-mode ultrasound images and the CESR ultrasound images only.

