9.0 STATISTICAL CONSIDERATIONS

This is a nonrandomized, single-center study. The primary purpose and endpoint of this study is to evaluate the sensitivity and specificity of CESR imaging in the analysis of known breast and thyroid lesions by comparing image analyses to the pathological results for these lesions.

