9.1 Study Design/Study Endpoints

This is a prospective study to assess the diagnostic performance of the newly developed device. The **primary outcome of interest is the sensitivity and specificity of the super-resolution imaging device in the analysis of known breast and thyroid lesions as compared to pathological results of these lesions**. The sensitivity and specificity can be estimated non-parametrically as the proportion of the lesions which are distinguished as malignant versus non-malignant compared to the reference. This estimate will be calculated for each reader then averaged over all the readers. The standard error of the average sensitivity and specificity estimate will be calculated using the bootstrap method, where each patient is treated as independent unit with 5 ratings. The confidence interval of the final estimate will be provided using the normality assumption.

Furthermore, we will estimate the sensitivity and specificity of the b-mode ultrasound in this study and compare it with the sensitivity and specificity estimate of the CESR imaging using the bootstrap approach and the confidence interval of their differences will be provided using the normality assumption.

Malignancy scores of +1 and +2 will be considered malignant. Scores of -2, -1, and 0 will be considered not malignant. The confidence of malignancy will be used independently

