9.2 Data Analysis Plans

ROC analysis will be performed as the primary analysis for the first aim. To compare the results from the two imaging modalities, we will adopt the mixed effect ANOVA based on the Dorfman-Berbaum-Metz method. The outcome variable is the Tukey's jackknife pseudovalues of the AUCs from each reader and each patient under either modality, and separately for each anatomic region. The fixed effect in the independent list will correspond to the difference between the two modalities and the random effects will be used to account for within-patient and within-reader's correlations.

Possible interactions between the modalities and the readers and the patients will also be included and tested for statistical significance. To test the main hypothesis, F-test statistic from the model parameter estimates will be used to compare the mean AUCs between the b-mode ultrasound images and the CESR ultrasound images only.

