12.0 APPENDICES

12.1 Appendix A: Reader Study Data Collection Form

Specimen: _____

Reader: _____

Date: _____

Overall Assessment:

Primary

Overall specimen malignancy score (-2 to +2): _____
Malignancy confidence (0-100) _____ %

Secondary

Overall specimen malignancy score (-2 to +2): _____
Malignancy confidence (0-100) _____ %

1. Primary versus Secondary Shape/Morphology

+3	I am significantly more confident in the Primary representation of the lesion shape/morphology I described as compared to Secondary representation of the same lesion
+2	I am more confident in the Primary representation of the lesion shape/morphology I described as compared to Secondary representation of the same lesion
+1	I am slightly more confident in the Primary representation of the lesion shape/morphology I described as compared to the Secondary representation of the same lesion.
0	I have the same confidence in the Primary representation of the lesion shape/morphology I described as I do in the Secondary representation of the same lesion
-1	I am slightly less confident in the Primary representation of the lesion shape/morphology I described as compared to the Secondary representation of the same lesion.
-2	I am less confident in the Primary representation of the lesion shape/morphology I described as compared to the Secondary representation of the same lesion.
-3	I am significantly less confident in the Primary representation of the lesion shape/morphology I described as compared to the Secondary representation of the same lesion.

2. Primary versus Secondary: Vascularity

+3	I am significantly more confident in the Primary representation of the lesion vascularity I described as compared to the Secondary representation of the same lesion.
+2	I am more confident in the Primary representation of the lesion vascularity I described as compared to Secondary representation of the same lesion
+1	I am slightly more confident in the Primary representation of the lesion vascularity I described as compared to the Secondary representation of the same lesion.
0	I have the same confidence in the Primary representation of the lesion vascularity I described as I do in the Secondary representation of the same lesion.
-1	I am slightly less confident in the Primary representation of the lesion vascularity I described as compared to the Secondary representation of the same lesion.

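### Does the 1-to-5 reader score in section 4.2.5 leave the primary sensitivity and specificity without a usable cut-off?

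*Combined protocol and SAP*

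**What the plan says.** Three places describe the reader's malignancy rating.

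- Section 4.2.5 (Reader Study): "The readers will be asked to assign a probability score (1 to 5"), together with "confidence for each lesion for each modality (0 to 100"%).
- Section 9.1 (Study Design/Study Endpoints), the dichotomy for the primary outcome: "Malignancy scores of +1 and +2 will be considered malignant. Scores of -2, -1, and 0 will be considered not malignant". On the second item it adds: "The confidence of malignancy will be used independently".
- Appendix A (section 12.1), the form the reader completes: "Overall specimen malignancy score (-2 to +2") and "Malignancy confidence (0-100"), each asked once for the Primary and once for the Secondary images.

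Section 9.0 states what the rating is for: "The primary purpose and endpoint of this study is to evaluate the sensitivity and specificity of CESR imaging". Section 9.2 also uses reader ratings, through "pseudovalues of the AUCs from each reader and each patient under either modality", without naming which rating feeds the curve.

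**The concern.** Section 4.2.5 and section 9.1 use different numbers for what should be the same rating. Taken literally, a reader following 4.2.5 would return values from 1 to 5, and 9.1 has no class for 3, 4 or 5. Worse, 1 and 2 share their digits with the +1 and +2 that 9.1 calls malignant, although on a probability scale they would be the low end. Nothing says that 5 is the most suspicious level, and no conversion is written.

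The threshold in 9.1 is the only one given for the primary endpoint. If it could not be applied to the data collected, someone would have to choose a cut-off after the scores were in. If the direction were also misread, the accuracy estimates and the comparison with b-mode would be turned round.

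**Working it through.** The plan gives no figure to reproduce here. The check is a comparison of texts, followed by a short argument about recoding.

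**Step 1: is it one rating or two?** Section 4.2.5 describes two items per lesion and modality: a five-level score and a 0-to-100% confidence. The form also has two items for each image set: a five-level score and a 0-to-100% confidence. The second items match and the first differ only in labels. This is one instrument described twice, and 4.2.5 is the outlier against 9.1 and Appendix A.

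**Step 2: does the form work with the 9.1 rule?** The form can yield -2, -1, 0, +1 or +2. Section 9.1 puts two of these in the malignant class and three in the other: 2 + 3 = 5, so every possible value is classified, each once. The form has no 1-to-5 field.

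**Step 3: what if scores came back as 1 to 5?** Let u be the 1-to-5 score and s = u - 3.

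| u (4.2.5) | s = u - 3 (form) | 9.1 class |
|---|---|---|
| 1 | -2 | not malignant |
| 2 | -1 | not malignant |
| 3 | 0 | not malignant |
| 4 | +1 | malignant |
| 5 | +2 | malignant |

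- Sensitivity is the share of malignant lesions with s ≥ +1. Since s ≥ +1 exactly when u ≥ 4, the same lesions are counted. Specificity is the share of benign lesions with s ≤ 0, that is u ≤ 3, and again the lesions are the same.
- AUC is P(malignant score > benign score) + ½ P(tie). It depends only on order and ties, and subtracting a constant changes neither.
- The bootstrap standard errors in 9.1 and the jackknife pseudovalues in 9.2 are built from these quantities, so they do not change either.

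**Step 4: illustration.** One simulated reader, with a latent AUC of 0.7 (the value section 9.3 assumes for conventional imaging) and assumed symmetric category boundaries:

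| Coding and cut | Sensitivity | Specificity | Five-level AUC |
|---|---|---|---|
| -2 to +2, 9.1 rule | 0.51 | 0.77 | 0.69 |
| 1 to 5, 4 and 5 malignant | 0.51 | 0.77 | 0.69 |

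The rows agree, as step 3 says they must for any data.

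**Step 5: which way does the 1-to-5 scale run?** Section 4.2.5 calls it a probability score, and objectives 2.2.1 and 2.2.2 describe the reader study as predicting malignancy. On the ordinary reading, higher means more probably malignant. Section 9.1 fixes the same direction for the form's scale: positive is malignant.

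**The case for a change.** The best case for acting is that using the form, and subtracting 3, are both inferences. Section 10.4 requires the study to be run exactly as the approved protocol describes, and 4.2.5 is part of that protocol. For the simulated reader above, calling 3 to 5 malignant gives sensitivity 0.76 and specificity 0.51. A scale used in descending order but read as ascending gives 0.24 and 0.49, with AUC 1 - 0.69 = 0.31. A primary threshold should not depend on a guess, and the correction would be one phrase.

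Part of this stands. The sentence in 4.2.5 is wrong as written, no conversion appears anywhere, and the direction of the 1-to-5 scale is not stated.

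The consequences do not stand.

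- Appendix A is equally part of the approved protocol, and it is the sheet on which the reader writes the score. Adherence to the protocol therefore includes using the form.
- Calling 3 to 5 malignant is not an open option, because 9.1 puts the middle level in the not-malignant class.
- The reversal needs a probability score on which higher means less probable, and an analyst who does not notice. Nothing in the documents suggests the first. The second is unlikely: the plan's assumed b-mode AUC of 0.7 would appear as 1 - 0.7 = 0.3, worse than chance.

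Two neighbouring gaps are separate from the scale mismatch. Section 9.2 does not say which rating feeds the AUC, and the form does not put words to its five malignancy levels. Changing the numbers in 4.2.5 would settle neither.

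**Conclusion.** The inconsistency is real but clerical. The form and the threshold for the primary endpoint already agree and cover every score the form can produce. On the form the numerical effect is zero. On a 1-to-5 scale running in the natural direction it is also zero after a one-step relabelling, which can be done after the reads and involves no choice of cut-off, since 9.1 has already placed the midpoint. No estimate, interval, test or sample-size figure in the plan changes.

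This rests on one of two conditions: that readers complete the Appendix A form, or, failing that, that a higher probability score means greater suspicion of malignancy. The documents support both and contradict neither beyond the one sentence in 4.2.5. Editing that sentence would tidy the text without altering any result, so no change to the plan is called for.

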5.0 INVESTIGATIONAL DEVICE

5.1 Investigational Device Description

Research Ultrasound Scanner: Verasonics Vantage 1024

Figu

Ultrasound 32 x 32 Transducer Arrays

[figure not shown]
[figure not shown]

similar

Figure 3. Vermon 32 x 32 matrix array.

Hybrid Dual-frequency Ultrasound Array

This dual-frequency imaging technique enables the detection of perflutren microbubbles without the need for spatiotemporal filtering.[22] Imaging with the dual-frequency probe will be performed with one Verasonics Vantage 256 system from the Vantage 1024 described above. For 3D acquisition, the transducer will be translated with a linear motion stage, as used in our previous study, LCCC 1748.

6.0 Perflutren Lipid Microspheres (Lantheus Medical Imaging)

[REDACTED]

6.1 Investigational Contrast Agent Description and Management

[REDACTED]

[REDACTED] [.com/pdf/vialmix-user-guide.pdf](https://www.definityimaging.com/pdf/vialmix-user-guide.pdf) and the package insert for instructions on the use of Vialmix®.

6.1.1 Known and Associated Risks

For indication see <https://www.definityimaging.com/pdf/definity-pi.pdf> and see section 1.8.2 for a summary of toxicities reported in clinical trials. In addition, the following warnings and precautions are noted in the January 2017 labeling:

Serious Cardiopulmonary Reactions:

Serious cardiopulmonary reactions including fatalities have occurred uncommonly during or shortly following perflutren-containing microsphere administration, typically within 30 minutes of administration. The risk for these reactions may be increased among patients with unstable cardiopulmonary conditions (acute myocardial infarction, acute coronary artery syndromes, worsening or unstable congestive heart failure, or serious ventricular arrhythmias). Always have cardiopulmonary

resuscitation personnel and equipment readily available prior to Definity® administration and monitor all patients for acute reactions. The reported reactions include: fatal cardiac or respiratory arrest, shock, syncope, symptomatic arrhythmias (atrial fibrillation, tachycardia, bradycardia, supraventricular tachycardia, ventricular fibrillation, ventricular tachycardia), hypertension, hypotension, dyspnea, hypoxia, chest pain, respiratory distress, stridor, wheezing, loss of consciousness, and convulsions.

Hypersensitivity Reactions:

In postmarketing use, serious hypersensitivity reactions were observed during or shortly following perflutren-containing microsphere administration including: Shock, bronchospasm, throat tightness, angioedema, edema (pharyngeal, palatal, mouth, peripheral, localized), swelling (face, eye, lip, tongue, upper airway), facial hypoesthesia, rash, urticaria, pruritus, flushing, and erythema have occurred in patients with no prior exposure to perflutren-containing microsphere products. Always have cardiopulmonary resuscitation personnel and equipment readily available prior to Definity® administration and monitor all patients for hypersensitivity reactions.

Systemic Embolization of Perflutren in Patients with Cardiac Shunts:

When administering Definity® to patients with a cardiac shunt, the microspheres can bypass filtering by the lung and enter the arterial circulation. Assess patients with shunts for embolic phenomena following Definity® administration. Definity® is only for intravenous administration; do not administer Definity® by intra-arterial injection.

Ventricular Arrhythmia Related to High Mechanical Index:

High ultrasound mechanical index values may cause microsphere cavitation or rupture and lead to ventricular arrhythmias. Additionally, end-systolic triggering with high mechanical indices has been reported to cause ventricular arrhythmias. Definity® is not recommended for use at mechanical indices greater than 0.8.

6.2 Return and Retention of Study Contrast Agent

Incomplete vials of perflutren lipid remaining at the completion of the study, or expired perflutren lipid will be destroyed by UNC IDS.

7.0 UNANTICIPATED CONCERNS (DEVICES)

7.1.1 Unanticipated Adverse Device Effect (UADE)

The investigational device exemption (IDE) regulations define an unanticipated adverse device effect (UADE) as "any serious adverse effect on health or safety or any life-threatening problem or death caused by, or associated with, a device, if that effect, problem, or death was not previously identified in nature, severity, or degree of incidence in the investigational plan or application (including a supplementary plan or

application), or any other unanticipated serious problem associated with a device that relates to the rights, safety, or welfare of subjects" (21 CFR 812.3(s)).

7.1.2 **Unanticipated Problems (UP)**

As defined by UNC's IRB, unanticipated problems involving risks to study subjects refers to any incident, experience, or outcome that:

- Is unexpected (in terms of nature, severity, or frequency) given (a) the research procedures that are described in the protocol-related documents, such as the IRB-approved research protocol and informed consent document; and (b) the characteristics of the subject population being studied;
- Is related or possibly related to a subject's participation in the research; and
- Suggests that the research places subjects or others at a greater risk of harm (including physical, psychological, economic, or social harm) related to the research than was previously known or recognized.

7.1.3 **Reporting**

7.1.4 **UADEs**

UADEs must be reported by the clinical investigator to the sponsor and the reviewing IRB, as described below:

For this device study, investigators are required to submit a report of a UADE to the FDA, the manufacturer of the device and the UNC IRB as soon as possible, but in no event later than 10 working days after the investigator first learns of the event (§ 812.150(a)(1)), using the MedWatch Form 3500A. Sponsors must immediately conduct an evaluation of a UADE and must report the results of the evaluation to FDA, the UNC IRB, and participating investigators within 10 working days after the sponsor first receives notice of the effect (§§ 812.46(b), 812.150(b)(1)).

For this device study, we will submit a report of a UADE to the manufacturer and the IRB as soon as possible, but no later than 10 working days after the investigators first learn of the event.

7.1.5 **UP**

Any events that meet the criteria for "Unanticipated Problems" as defined by UNC's IRB must be reported by the Study Coordinator using the IRB's web-based reporting system.

Any unanticipated problem that occurs during the conduct of this study and that meets **at least** the first two criteria listed in section 7.1.2 must be reported to the UNC IRB using the IRB's web-based reporting system.

8.0 ADVERSE EVENTS (DRUGS- CONTRAST AGENTS)

8.1 Definitions

8.1.1 Adverse Event (AE)

An adverse event (AE) is any untoward medical occurrence (e.g., an abnormal laboratory finding, symptom, or disease temporally associated with the use of a drug) in a patient or clinical investigation subject administered a pharmaceutical product and which does not necessarily have a causal relationship with this treatment. An AE can therefore be any unfavorable and unintended sign (including an abnormal laboratory finding), symptom, or disease temporally associated with the use of a medicinal product, whether or not related to the medicinal product.

Hospitalization for elective surgery or routine clinical procedures that are not the result of an AE (e.g., surgical insertion of central line) need not be considered AEs and should not be recorded as an AE. Disease progression should not be recorded as an AE, unless it is attributable by the investigator to the study therapy.

8.1.2 Suspected Adverse Reaction (SAR)

A suspected adverse reaction (SAR) is any AE for which there is a *reasonable possibility* that the drug is the cause. *Reasonable possibility* means that there is evidence to suggest a causal relationship between the drug and the AE. A suspected adverse reaction implies a lesser degree of certainty about causality than adverse reaction, which means any adverse event caused by a drug.

Causality assessment to a study drug is a medical judgment made in consideration of the following factors: temporal relationship of the AE to study drug exposure, known mechanism of action or side effect profile of study treatment, other recent or concomitant drug exposures, normal clinical course of the disease under investigation, and any other underlying or concurrent medical conditions. Other factors to consider in considering drug as the cause of the AE:

- Single occurrence of an uncommon event known to be strongly associated with drug exposure (e.g., angioedema, hepatic injury, Stevens-Johnson Syndrome)
- One or more occurrences of an event not commonly associated with drug exposure, but otherwise uncommon in the population (e.g., tendon rupture); often more than once occurrence from one or multiple studies would be needed before the sponsor could

determine that there is *reasonable possibility* that the drug caused the event.

- An aggregate analysis of specific events observed in a clinical trial that indicates the events occur more frequently in the drug treatment group than in a concurrent or historical control group

